APPENDIX I SAMPLE SAS CODE IN STATISTICAL ANALYSIS

1) Sample Code for Efficacy Analysis : Schirmer test I

An Analysis of variance will be used for Schirmer test I, followed by Williams test. An example of the SAS code to perform this analysis is below.

```
*****
* SAS Code: GLM (Analysis of variance) followed by William test
* Variables in the model:
*&var=CHG = Change from baseline in Schirmer test I at week 4
*&trt=trt01p = treatment planned
*****,
%macro WILLIAMS(dat = , trt = , var = );
/*##### WILLIAMS TEST #####*/
/*For Williams Test, We Assume a Monotonic Dose Relationship (i.e. x0 <= x1 <= x2 <=... x7 etc.). If this does not occur, then a dose that does not conform (when sorted by dose level) should be combined with next closest dose and averaged. Keep doing this until we get conformance. Note that this relies on comparing vs x0, so x0 should always be lowest result*/
%global lsm1 maxdose contmean;
/*Assign a New Dose Number (Consecutive) for Processing*/
proc sort data = &dat. out = DOSEN (keep = &trt.) nodupkey;
  by &trt.;
run;
data DOSEN;
  set DOSEN;
  DOSEN = _N_;
run;
data &dat.2;
  merge &dat. DOSEN;
  by &trt.;
run;
```

This document is confidential.

```
proc glm data = &dat.2 noprint outstat=STAT_(keep = _TYPE_ DF SS where=(_TYPE_="ERROR"));
  class DOSEN;
  model &var. = DOSEN;
  lsmeans DOSEN / pdiff cl;
  output out = STAT p=LSMEAN r=resid LCL=LCI UCL=UCI STDP=STDERR;
run;

proc sort data = STAT out = STAT2 (keep = &trt. DOSEN LSMEAN LCI UCI STDERR) nodupkey;
  by DOSEN;
run;

/*Get Max Dose Level for Processing*/
proc sql noprint;
  select compress(put(max(DOSEN),best.)) into :MAXDOSE
  from STAT2;
quit;
%put &maxdose.;

/*Get LSMEAN for Placebo/Control for Processing*/
proc sql noprint;
  select compress(put(LSMEAN,best.)) into :CONTMEAN
  from STAT2(where=(DOSEN=1));
quit;
%put &contmean.;

/*Get Number of Observations and Merge Back on to GLM Output*/
proc univariate data = STAT noprint;
  by DOSEN;
  var RESID;
  output out = N N=N;
run;

data STAT_2 (drop = _TYPE_ SS);
  set STAT_;
  if nmiss(DF,SS) = 0 then MSE = SS/DF;
  do DOSEN = 1 to &maxdose.;
    output;
  end;
run;

data STAT2;
  merge STAT2(in=a) N STAT_2;
  by DOSEN;
  if a;
run;

/*Get Dose Level 1 LSMean for Checking Whether Each Dose >= Dose1*/
proc sql noprint;
  select compress(put(LSMEAN,best.)) into :LSM1
```

This document is confidential.

```
from STAT2(where=(DOSEN=1));
quit;
%put &lsm1.;

/*Output All LSMEANS and N for All Dose Levels Present*/
%macro VAR(var = );
proc sort data = STAT2;
  by MSE DF;
run;
proc transpose data = STAT2 out = STAT2_&var.(drop = _NAME_) prefix=&var.;
  by MSE DF;
  id DOSEN;
  var &var.;
run;
%mend VAR;
%VAR(var = LSMEAN); %VAR(var = N);

data STAT3(drop = _LABEL_);
  merge STAT2_LSMEAN STAT2_N;
run;

data STAT4;
  set STAT3;
  array LSMEAN(&maxdose.); array N(&maxdose.); array DIFF(&maxdose.); array
DENOM(&maxdose.);
  array T(&maxdose.);
  CONTROL = LSMEAN(1);
  do j = 1 to &maxdose.-1;
    if LSMEAN(j) > LSMEAN(j+1) then do;
      EN = N(j+1);
      EMEAN = LSMEAN(j+1);
      NMEAN = N(j+1)*LSMEAN(j+1);
      do k = j to 1 by -1;
        if EMEAN < LSMEAN(k) then do;
          EN = EN + N(k);
          NMEAN = NMEAN + N(k)*LSMEAN(k);
          *EMEAN = (EMEAN*N(k)/(EN)) + ((N(k)*LSMEAN(k))/(EN));
          EMEAN = NMEAN/EN;
          do r = k to j+1;
            LSMEAN(r) = EMEAN;
          end;
        end;
      end;
    end;
  end;
  do j = 2 to &maxdose.;
    DIFF(j) = (LSMEAN(j)-CONTROL);
    DENOM(j) = ((MSE*((1/N(j))+(1/N(1))))**0.5);
    T(j) = DIFF(j)/DENOM(j);
  end;
run;
```

This document is confidential.

```
data STAT5 (drop = EMEAN EN MSE DF j k r DIFF: DENOM:);
  set STAT4;
  array LSMEAN(&maxdose.); array T(&maxdose.); array p(&maxdose.);
  do i = 2 to &maxdose.;
    p(i) = 1 - probmc("Williams",T(i),,DF,i-1);
  end;
run;

%macro OUT(var2=, dat = , out = );
data &out.(keep = DOSE.);
  set &dat.;
  %do i = 1 %to &maxdose.;
    rename &var2.&i.=DOSE&i.;
  %end;
run;
%mend OUT;

%OUT(var2 = LSMEAN, dat = STAT3, out = LSMEAN1);
%OUT(var2 = LSMEAN, dat = STAT5, out = LSMEAN2);
%OUT(var2 = N, dat = STAT5, out = N);
%OUT(var2 = T, dat = STAT5, out = T);
%OUT(var2 = P, dat = STAT5, out = P);

data WILLIAMS (keep = TYPE DOSE1-DOSE&maxdose.);
  retain TYPE DOSE1-DOSE&maxdose.;
  length TYPE $50.;
  set LSMEAN1(in=a) LSMEAN2(in=b) N(in=c) T(in=d) P(in=e);
  if a then TYPE = "LSMeans (Original)";
  if b then TYPE = "MLE";
  if c then TYPE = "No. Obs";
  if d then TYPE = "Williams T Statistic";
  if e then TYPE = "P-Value";
run;
%mend WILLIAMS;
```

This document is confidential.

2) Sample Code for Efficacy Analysis : Schirmer test I in case of presence of many missing data

For RMM, if SAS mixed model is used, the sample SAS codes will be like the following:

```
PROC MIXED DATA=SCHIRMERI;
CLASS usubjid TRT01P visit;
MODEL chg = TRT01P TRT01P * visit /ddfm=kr;
repeated visit / sub = usubjid type = un;
lsmeans TRT01P / cl diff at time = Week4;
```

3) Sample Code for Exploratory sensitivity Efficacy Analysis : Schirmer test I

```
PROC MIXED DATA=SCHIRMERI;
CLASS STRATA TRT01P ;
MODEL chg = TRT01P STRATA STRATA*TRT01P /solution;
lsmeans STRATA*TRT01P / pdiff cl at time=Week4;
```

4) Sample Code for Efficacy Analysis : IDEEL and EQ-5D-3L

```
PROC MIXED DATA=IDEEL;
CLASS usubjid TRT01P visit;
MODEL chg = TRT01P visit TRT01P * visit /ddfm=kr;
repeated visit / sub = usubjid type = un;
lsmeans TRT01P*visit / cl pdiff;
lsmeans TRT01P / cl pdiff;
```

5) Sample Code for Efficacy Analysis: PGIC

A Wilcoxon rank sum test will be used for PGIC. An example of the SAS code to perform this analysis is reported below.

```
*****
```

* SAS Code: Wilcoxon

* Variables in the model:

* aval = value of PGIC

*trt01pn = treatment planned

```
*****;
```

```
PROC NPAR1WAY DATA=PGIC WILCOXON;
WHERE TRT01P in ("Placebo" "Dose 1");
CLASS TRT01P;
VAR AVAL;
RUN;
```

6) Sample Code for Efficacy Analysis: Proportion of subjects with worsening in SANDE and/or NEI score>=50%

```
*****
```

This document is confidential.

* SAS Code: Wilcoxon

* Variables in the model:

* aval = worsening in symptom scores (SANDE) and/or NEI score $\geq 50\%$: yes or No

*trt01pn = treatment planned

*****;

```
PROC FREQ DATA=Prop;
  WHERE TRT01P in ( "Placebo" "Dose 1");
  TABLES trt01p*aval / chisq;
  RUN;
```

This document is confidential.

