8.1. Primary Efficacy Endpoint and Analysis

The primary efficacy endpoint is the change from baseline in Schirmer test I (without anesthesia) versus Week 4. The primary analysis is based on the FAS population. Missing data will be replaced by means of the Last Observation Carried Forward (LOCF) method.

The Schirmer test I will be summarized using descriptive statistics for continuous variables by treatment and visit. The change from baseline value will also be summarized for all post-baseline visits. The same summary analysis will be provided after pooling the treated patients (20 µg/mL BID arm and 20 µg/mL TID) together. Comparison (descriptive in nature) of the change from baseline of each treatment versus placebo will be performed by means of a t-test at each timepoint.

The primary analysis will be performed by means of an analysis of variance including only treatment as main factor followed by pre-planned comparisons from Vehicle and rhNGF dosages according to Williams' procedure.

The first comparison will compare the rhNGF TID dose to the Placebo using Williams test.

In case of significant result then the rhNGF BID dose will be compared to the Placebo; if the result is not significant then the test will be stopped.

Description of the Williams' Test:

μ_0 = Effect of Placebo

μ_1 = Effect of rhNGF BID

μ_2 = Effect of rhNGF TID

Hypotheses:

$H_0: \mu_0 = \mu_1 = \mu_2$

$H_1: \mu_0 <= \mu_1 \leq \mu_2$

The test develops into two phases:

* First step

Starting from the observed means X_i , determine the maximum likelihood estimates M_i (corrected mean of group i after amalgamation) under the alternative hypothesis.

If X_i satisfies the inequalities written in H_1 then $M_i = X_i$

Otherwise pool any adjacent violators into the same value:

$M_i = (n_i * X_i + n_{i+1} * X_{i+1}) / (n_i + n_{i+1})$ where n_i = sample size of group i.

The process is repeated until the means are completely ordered.

This document is confidential.

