| 20. Headaches associated with dry eye symptoms | Symptom Bother | IDLSYM20 | Yes |

This document is confidential.

| Response for question 1 (IDLSYM1) | Original response code | Item score |
|-----------------------------------|------------------------|------------|
| None of the time | 0 | 0 |
| A little of the time | 1 | 1 |
| Some of the time | 2 | 2 |
| Most of the time | 3 | 3 |
| All of the time | 4 | 4 |

| Response for questions 2 to 20 (IDLSYM2 - IDLSYM20) | Original response code | Item score |
|---|------------------------|------------|
| I did not have this symptom / Not applicable | 0 | 0 |
| Not at all | 1 | 1 |
| Slightly | 2 | 2 |
| Moderately | 3 | 3 |
| Very much | 4 | 4 |

All questions (IDLSYM1 – IDLSYM20) are included in the Symptom Bother scale score (IDLSYM).

If 50% (10) or fewer of the 20 questions used in the calculation of Symptom Bother scale score have missing item scores, then the scale score is calculated by multiplying the mean of the non missing item score by 25. If 11 or more of the 20 item scores are missing then the scale score is not calculated and should be set at missing.

Multiplying by 25 transforms the scale score to a 0 to 100 scale, with 0 reflecting the greatest degree of treatment related bother measurable by the scale and 100 reflecting the lowest degree of treatment-related bother.

Changes from baseline in each scale score will be analyzed using an mixed model for repeated measures (MMRM). The analyses will include the fixed, categorical effects of treatment (3 levels: rhNGF 20 µg/ml TID, rhNGF 20 µg/ml BID and vehicle TID), visit (4 levels: Weeks 4, 8, 12, 16) and treatment by visit interaction. Subject will be considered as a random effect. The covariance matrix used will be "unstructured". Comparisons versus vehicle TID will be provided using least square means at each visit and overall.

IDEEL data will be also listed.

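### The sample Williams macro does not ensure that vehicle is the control arm: it takes whichever TRT01P label sorts first, and two of the SAP's namings put vehicle last

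*SAP*

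**What the plan says.** SAP 8.1 specifies the primary test clearly. Index 0 is defined as "Effect of Placebo", index 1 as BID and index 2 as TID. The first comparison is TID against placebo, and BID is tested only if that is significant. The statistic subtracts the observed placebo mean.

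Appendix I, item 1, gives SAS code for this test. Its header sets the treatment argument: "trt=trt01p = treatment planned". The macro then:

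- reduces the data to the distinct values of that variable by sorting: "proc sort data = &dat. out = DOSEN (keep = &trt.) nodupkey";
- sets the arm number DOSEN to the row number `_N_`;
- takes DOSEN = 1 as the control, under the comment "Get LSMEAN for Placebo/Control for Processing";
- later sets "CONTROL = LSMEAN(1" and forms every T statistic against that mean.

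The SAP names the arms in at least three ways:

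- Appendix I, item 5, filters with "WHERE TRT01P in ('Placebo' 'Dose 1", and item 6 filters on the same two values. TRT01P is therefore treated as a character variable. These are the only literal TRT01P values in the SAP.
- SAP 8.2.6 lists the treatment levels of the repeated-measures model as rhNGF 20 µg/ml TID, then "rhNGF 20 µg/ml BID and vehicle TID". SAP 8.2.8 lists the same levels.
- SAP 8.1 uses Placebo, rhNGF BID and rhNGF TID.

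No section gives the full list of TRT01P values in the analysis dataset.

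**The concern.** Williams' procedure needs two facts about the arms: which one is the zero dose, and in what order the doses rise. The macro takes both from the spelling of a label. A comment in it speaks of sorting by dose level, but nothing in the code makes alphabetical order agree with dose order.

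If vehicle sorts last, the macro uses an active arm as the control and treats vehicle as the top dose. The amalgamation step then pools means in the wrong direction, and the first-step statistic no longer compares TID with vehicle. The final output dataset keeps only columns numbered DOSE1, DOSE2 and DOSE3, without treatment names, so the error would not show on the face of that output. The same code would serve the secondary endpoints that the SAP analyses in the same way as Schirmer test I.

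**Working it through.** **1. The plan's own figure.** Inputs from SAP 3.4: difference 5.3 mm, SD 10.78, one-sided alpha 0.025, power about 90%.

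n per group = 2 × (1.960 + 1.282)² × (10.78 / 5.3)² = 86.9, so 87. This matches the SAP. With 76 per group, the SE of a difference is 10.78 × √(2/76) = 1.749 and 5.3 / 1.749 = 3.031. Power is Φ(3.031 − 1.960) = 0.858, which agrees with the SAP's at least 85%.

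**2. Sort order of each naming.** ASCII order is assumed. The results are the same if case is ignored.

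| Source of names | Sorted order | Arm used as control |
|---|---|---|
| Appendix I, items 5 and 6 (Dose 2 assumed) | Dose 1, Dose 2, Placebo | Dose 1 |
| SAP 8.2.6 and 8.2.8 | rhNGF 20 µg/ml BID, rhNGF 20 µg/ml TID, vehicle TID | BID |
| SAP 8.1 | Placebo, rhNGF BID, rhNGF TID | Placebo (correct) |

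For a capitalised Vehicle paired with rhNGF labels, the result depends on collation: first in ASCII order, last if case is ignored.

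**3. One worked case.** Take 87 per group and observed means of 0 for vehicle and 5.3 for each dose. The SE is 10.78 × √(2/87) = 1.634.

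- Correct order (0, 5.3, 5.3): nothing is pooled. T = 5.3 / 1.634 = 3.24 for both doses.
- Order BID, TID, vehicle (5.3, 5.3, 0): the last two are pooled to 2.65, which is below 5.3, so all three are pooled to 10.6 / 3 = 3.53. The control keeps its observed mean of 5.3. T = (3.53 − 5.3) / 1.634 = −1.08 for both positions.

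**4. Rejection rates at the first step.** The macro's numbering, amalgamation and T statistic were simulated with SD 10.78. The two-dose Williams critical value at one-sided 0.025, also found by simulation, was 2.027 for 76 per group and 2.019 for 87. In the wrong order the position tested first is vehicle and the comparator is BID.

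| True means, vehicle / BID / TID | n per group | Correct order | Order BID, TID, vehicle |
|---|---|---|---|
| 0 / 5.3 / 5.3 | 76 | 0.91 | about 0 |
| 0 / 5.3 / 5.3 | 87 | 0.94 | about 0 |
| 0 / 2.65 / 5.3 | 76 | 0.85 | 0.009 |
| 0 / 2.65 / 5.3 | 87 | 0.89 | 0.010 |
| 0 / −5.3 / −5.3 | 76 | about 0 | 0.84 |
| 0 / 0 / 0 | 76 | 0.024 | 0.024 |

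The 0.84 can be checked by hand. Vehicle truly exceeds the false control by 5.3 mm, so the rate is about Φ(3.031 − 2.027) = Φ(1.004) = 0.84.

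**The case against.** The strongest reply is that SAP 8.1 is unambiguous and the code is not. The appendix is headed as sample code and calls the macro an example. The treatment variable is a macro argument, so a suitably ordered variable could be passed instead. The comments in items 5 and 6 name trt01pn, which suggests that a numeric treatment code was in mind. Dose 1 may be only a placeholder, and the lower-case vehicle in 8.2.6 may be ordinary prose rather than a data value. SAP section 14 requires double programming with electronic comparison. The macro's output includes the original means and the group sizes, which would disagree with the by-treatment summary in Table 14.2.1.5.1 if the arms were swapped.

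Most of this stands, and it keeps the point small. A reader might infer that every naming in the SAP mis-sorts, or that the primary test will compare the wrong arms. The documents support neither: the names in the Williams description itself sort correctly, and the dataset labels are not given.

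Two things remain. The code for the primary test selects the wrong comparator when given the appendix's own TRT01P values. And comparing the real arm means is possible only after unmasking, when correcting the primary analysis is awkward to explain. The trt01pn comments do not settle the matter, because the code beneath them uses TRT01P.

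**Conclusion.** The point holds as a gap in the sample code, of low severity. The planned analysis in SAP 8.1 is correctly specified; the macro does not guarantee that it is what gets run. Two of the three namings tabulated above put vehicle last and one gives the intended order.

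The cost is large but conditional. At 76 per group, first-step rejection goes from about 91% to about 0% if both doses are 5.3 mm better, and from about 0% to about 84% if both are 5.3 mm worse. These figures assume unmodified code, mis-sorting labels, a Dose 2 label for the first naming, the SAP's SD and difference, and the stated true BID means. They say nothing about how likely the error is.

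Two further inferences should be resisted. The error does not inflate type I error under the global null, where the rate stays near 0.025. And the better/worse reading applies to endpoints where a higher value is favourable, such as Schirmer test I; it does not carry over to SANDE or the staining score.

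**What to change.** - Define in the SAP a numeric dose order for the Williams test: vehicle = 0, BID = 1, TID = 2. State that it is separate from the table display order, because SAP 13.2.4 puts active treatment before vehicle and a code built for display would repeat the fault.
- In the macro, set DOSEN to that code plus 1 instead of the sort position.
- Add a check before PROC GLM that stops the program unless DOSEN = 1 is vehicle.
- Use one set of treatment labels throughout the SAP, and make the comments and code in items 5 and 6 name the same variable.

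This costs a few lines of code and text. It changes no hypothesis, alpha level or endpoint, and should be done before unmasking.

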8.2.8. EQ-5D-3L

EQ-5D-3L will be collected at screening, baseline, Week 4, Week 8, Week 12 and Week 16.

The Questionnaire EQ-5D-3L is a 5-dimension instrument assessing quality of life. The 5 dimensions are Mobility, Self-Care, Usual Activity, Pain/Discomfort, and Anxiety/Depression. Each dimension is scored as 1 = no problem, 2 = some problem, and 3 = extreme Problem.

No imputation will be done on missing values.

Descriptive summary statistics for the single dimension scores ("Mobility", "Self-Care", "Usual Activities", "Pain/Discomfort" and "Anxiety/Depression") will be presented by visit and treatment group.

Shift tables comparing results from Baseline to each visit will be presented with percentages based on subjects with a non-missing value at Baseline and post-baseline visit.

The patients provide an assessment of their best health state by means of a score between 0 and 100 (EQ visual analogue scale – VAS).

The change in VAS score from the baseline visit to the post-baseline visit will be analyzed using an mixed

model for repeated measures (MMRM). The analyses will include the fixed, categorical effects of treatment (3 levels: rhNGF 20 µg/ml TID, rhNGF 20 µg/ml BID and vehicle TID), visit (4 levels: Weeks 4, 8, 12, 16) and treatment by visit interaction. Subject will be considered as a random effect. The covariance matrix used will be "unstructured". Comparisons versus vehicle TID will be provided using least square means at each visit and overall.

EQ-5D-3L data will be listed.

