9.7. Physical Examination

Not applicable

This document is confidential.

10. Interim Analyses

No interim analysis was planned

This document is confidential.

11. Changes from Analysis Planned in Protocol

IDEEL and EQ-5D will be analysed using a mixed model for repeated measures (MMRM) instead of analysis of variance as the method seems more appropriate due to the repeated measures.

Exploratory sensitivity analysis will be also conducted for SANDE, Schirmer Test II, Corneal and Conjunctiva Vital Staining and TFBUT instead of only primary efficacy endpoint.

Overall compliance will not be calculated, as we don't have in the database the number of unused vials. We only have the number of vials not returned to the site whatever the reasons

Additional analyses have been planned to investigate the impact of COVID-19 pandemic on primary endpoint and on patient safety profiles (in case of 10% randomized patients affected).

Summary statistics on primary endpoint reporting the two treatment doses (20 µg/mL BID arm and 20 µg/mL TID) pooled versus placebo has been added to see the overall effect of the rhNGF treatment.

A sensitivity analysis on primary endpoint based on classification of patients in "Responders" and "Non Responders" based on the Schirmer Test I at the end of treatment has been added. This analysis will assess the robustness of results by considering an exact statistical method (not depending on assumption of normality of the data) and based on the status of the patients at the end of treatment.

This document is confidential.

12. Reference List

1. Williams DA. The comparison of several dose levels with a zero dose control. 1972. Biometrics 28, 519-531.
2. Williams DA. A test for differences between treatment means when several dose levels are compared with a zero dose control. 1971. Biometrics 27, 103-117.
3. Shein-Chung Chow, Jun Shao, Hansheng Wang; Samples Size Calculations in Clinical Research - Marcel Dekker, Inc. 2003I, SBN: 0-8247-0970-5, p. 186-189.
4. F Amparo, DA Schaumberg, R Dana; Comparison of two questionnaires for dry eye symptom assessment: the ocular surface disease index and the symptom assessment in dry eye Ophthalmology 2015 July; 122 (7), 1498 - 1503

This document is confidential.

13. Programming Considerations

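### The IDEEL and EQ VAS repeated-measures models leave out the baseline score: the contrast stays unbiased, but precision is lost and chance baseline imbalance is over-corrected

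*SAP*

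**What the plan says.** For IDEEL, SAP 8.2.6 makes change from baseline in each scale score the outcome of a mixed model for repeated measures. It states: "The analyses will include the fixed, categorical effects of treatment", followed by "visit (4 levels: Weeks 4, 8, 12, 16) and treatment by visit interaction". Six scales are scored: Daily Activity Limitations, Emotional Well-Being, Work Limitations, Treatment Satisfaction/Happiness, Treatment-Related Bother and Symptom Bother.

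For the EQ VAS, SAP 8.2.8 has the same structure: "The change in VAS score from the baseline visit to the post-baseline visit will be analyzed using an mixed" model, with the same three fixed effects. For both instruments the results to be reported are set out in the same way: "Comparisons versus vehicle TID will be provided using least square means at each visit and overall".

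The sample code for both (Appendix I item 4) agrees with the text: "MODEL chg = TRT01P visit TRT01P * visit /ddfm=kr". The omission is therefore the stated model and not shortened example code.

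Baseline is available. For the EQ-5D-3L, "EQ-5D-3L will be collected at screening, baseline, Week 4, Week 8, Week 12 and Week 16", and SAP 8.2.6 and the flowchart in SAP 3.7 show the same for IDEEL at Day 1.

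SAP section 11 explains the move away from the protocol's method: "IDEEL and EQ-5D will be analysed using a mixed model for repeated measures (MMRM) instead of analysis of variance". The reason given is the repeated measures; baseline adjustment is not mentioned. Protocol 9.5 had these endpoints follow the primary analysis, an analysis of variance on treatment alone. The absence of a baseline term carries over from there.

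**The concern.** Subtracting the baseline value does not remove its influence. Through regression to the mean, patients who start worse tend to show larger improvements, so the change stays correlated with baseline. With no baseline term, that variation goes into the residual and widens every standard error. In any one realised trial, an arm that happens to start worse also gains an apparent advantage.

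At stake are the comparisons of each active arm with vehicle for seven outcomes (six IDEEL scales and the VAS), at four visits and overall. Enrolment stopped at 261 instead of 300, so precision is already lower than planned. A correction to the primary Schirmer test I analysis would not reach these outcomes, because they have their own model.

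**Working it through.** **The plan's own figures.** No sample size, power or standard deviation is given for IDEEL or EQ VAS. The figures in SAP 3.4 concern Schirmer test I and do not depend on this model. They reproduce: with delta 5.3, SD 10.78, one-sided 0.025 and 90% power, n = 86.94, so 87 per group. Power at 76 per group is 85.8%, against the stated minimum of 85%. I use 76 per arm below only as a reference size.

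**Assumptions.** The baseline-to-visit correlation ρ is not in the documents. I take 0.3 to 0.9, with equal variance σ² at baseline and follow-up.

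**Single visit, precision.**
- Variance of the change: 2σ²(1 − ρ).
- Variance after baseline adjustment: σ²(1 − ρ²).
- Difference: σ²(1 − ρ)². This is zero only when the slope of follow-up on baseline is 1.
- Ratio, adjusted to unadjusted: (1 + ρ)/2. The standard error falls by 1 − √((1 + ρ)/2).
- Adjusted sample size that gives the same precision as 76 per arm unadjusted: 76(1 + ρ)/2.
- Power of the unadjusted contrast when the adjusted one has 80% (two-sided 0.05): Φ(2.802·√((1 + ρ)/2) − 1.960).

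**Single visit, imbalance.** Given a baseline difference d between arms, the change contrast shifts by (ρ − 1)d. At 76 per arm, a difference of one standard error is √(2/76) = 0.162 SD.

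| ρ | Variance ratio | SE reduction | 76 unadjusted is worth | Power unadjusted | Shift from a 1-SE imbalance |
|---|---|---|---|---|---|
| 0.3 | 0.65 | 19% | 49 | 62% | −0.11 SD |
| 0.5 | 0.75 | 13% | 57 | 68% | −0.08 SD |
| 0.7 | 0.85 | 8% | 65 | 73% | −0.05 SD |
| 0.9 | 0.95 | 3% | 72 | 78% | −0.02 SD |

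The negative sign means that the arm with the worse baseline gains, whichever way the scale runs.

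**Overall contrast.** Assume in addition that all five time points are equally correlated. The mean of the four post-baseline visits then has variance σ²(1 + 3ρ)/4. The change has variance (1 + 3ρ)/4 + 1 − 2ρ and the adjusted value (1 + 3ρ)/4 − ρ², both in units of σ². The adjusted-to-unadjusted ratios are:
- ρ = 0.3: 0.385/0.875 = 0.44
- ρ = 0.5: 0.375/0.625 = 0.60
- ρ = 0.7: 0.285/0.375 = 0.76
- ρ = 0.9: 0.115/0.125 = 0.92

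Under this pattern the loss is larger for the overall contrast than for a single visit.

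**Simulation check** (76 per arm, baseline plus four visits, equal correlation, complete data; ρ = 0.3, 0.5, 0.7):
- Week 4 variance ratio, unadjusted to adjusted: 1.54, 1.33, 1.17. The formula 2/(1 + ρ) gives 1.54, 1.33, 1.18.
- Overall ratio: 2.27, 1.62, 1.29. The expressions above give 2.27, 1.67, 1.32.
- Slope of the change contrast on baseline imbalance: −0.71, −0.51, −0.31 unadjusted, and about −0.01 adjusted.

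**The case against.** The other side has four fair points.

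- **The analysis is valid.** A reader might infer that chance baseline imbalance goes uncorrected, or that the contrast is biased. The documents do not support that. The outcome is a change score, so baseline is already subtracted in full. What remains is an over-correction with slope ρ − 1, and over repeated randomisations the contrast is unbiased. The point concerns efficiency and conditional bias only.
- **The size is unknown.** Neither ρ nor equality of variances is documented for these instruments. At ρ = 0.9 the single-visit gain is only about 3%. This stands: the direction is secure whenever the slope differs from 1, but the magnitude is conditional.
- **The plan is consistent with itself.** The protocol specified a treatment-only analysis, and the SAP discloses its move to a repeated-measures model. These are secondary endpoints in a Phase II trial with no power claim attached. This limits the weight of the point. It is not a reason to keep the less precise model when the baseline score is already in hand.
- **The stratum matters less than it seems.** Because randomisation is described as stratified, a reader might see the missing Primary Sjögren term as an equal fault. SAP 3.5 reports 135 patients randomised by the beginning of September, before the stratified list came into use. That is 135/261 = 52% of the final total. Their stratum comes from the medical history form under the SAP 8.1 rule. IDEEL and EQ health-score tables by stratum are also planned; these are displays and not adjustment, but the factor is not ignored.

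**Conclusion.** The concern holds as a matter of precision and conditional bias, not of validity. Text and code agree that the models for the six IDEEL scales and the EQ VAS contain no baseline score, and no sensitivity analysis of these endpoints adds one. The exploratory stratum analysis that SAP 8.2 extends to other secondary endpoints does not cover them.

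With equal variances and ρ between 0.3 and 0.9, the unadjusted single-visit standard errors are larger than they need be; adjustment would cut them by about 19% down to 3%. Under equal correlations the overall contrast would gain more. The certainty attaches to the omission and the direction. The size rests on correlations that the documents do not give. The change is worth making because it is nearly free, but the planned analysis would not mislead on average without it.

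**What to change.** In SAP 8.2.6 and 8.2.8, add the baseline score and its interaction with visit to the listed fixed effects. In Appendix I item 4 use:

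`MODEL chg = base base*visit TRT01P visit TRT01P*visit / ddfm=kr;`

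Here `base` is the patient's baseline value of the score being analysed. It is continuous, so it stays out of the CLASS statement. Centre it at its mean, or take the least-squares means at the mean baseline. Record the change in SAP section 11, since it departs from the treatment-only analysis in the protocol, and make it before unmasking.

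Optionally, add the Primary Sjögren stratum as a main effect. It must then be listed in the CLASS statement of item 4, with the SAP 8.1 medical-history rule applied to patients randomised before the amendment. Its precision gain is not quantified here.

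The cost is an edit to two text sections, one code block and the list of changes. No new data are needed. A patient without a baseline value has no change score, so adding the covariate excludes nobody.
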